#### 8.1.2 Serious Adverse Events

A serious adverse event (SAE) is defined as any untoward medical occurrence that at any dose:

- 1. **Results in death** The event must be the cause of death for the SAE to meet this serious criterion.
- 2. **Is life-threatening** The term "life-threatening" refers to an event in which the subject was at risk of death at the time of the event; it does not refer to an event that hypothetically might have caused death if it had been more severe.
- 3. **Requires in-patient hospitalization or prolongation of existing hospitalization** The sponsor considers "hospitalization or prolongation of existing hospitalization" for at least 24 hours as the defining criterion for an SAE. Hospital admissions for planned surgery or for normal disease management procedures (eg, chemotherapy) are not considered as defining criteria for SAEs.
- 4. Results in persistent or significant disability or incapacity.
- 5. Is a congenital anomaly or birth defect.
- 6. **Is medically significant** A medically significant event is defined as an event that does not meet any of the other 5 SAE criteria, but which is judged by a physician to potentially jeopardize the subject or require medical or surgical intervention to prevent one of the above outcomes listed as an SAE criterion. Anaphylaxis that is successfully treated by administration of epinephrine prior to other sequelae is an example of a potentially medically important event.

For the purpose of data collection in this study, a prolonged seizure or series of seizures from which the subject does not regain consciousness between ictal events, that is at least 30 minutes in duration, is termed status epilepticus (SE). A single episode of SE in a 24-hour period,

Confidential Page 71 of 175

regardless of whether rescue medication was administered, should be entered in the AE log as well as in the seizure diary. If two or more episodes occur within 24 hours, each lasting 30 As nonserio

A seport [2011]), the sponso.

A (Table 10).

A (Tabl minutes or more, an SAE of SE should be recorded. Hospitalization to manage SE, regardless of the number of episodes, should be reported as an SAE.

Adverse events that do not fall into the above categories are defined as nonserious AEs.

As per ICH guidance (E2F Development Safety Update Report [2011]), the sponsor has

Confidential Page 72 of 175

# **Table 10:** Adverse Events of Special Interest

#### CV/Respiratory

- Chest pain any pain in sternal area that is described for example as crushing, burning, sharp, stabbing or dull.
- Dyspnea/shortness of breath any signs of difficult or labored breathing unrelated to a previous medical condition that has not worsened.
- 3. Persistent cough longer than 4 weeks without a confirmed identified pathogen (or any other persistent cough that the investigator feels is suspicious).
- 4. Increase in blood pressure >30% from Screening blood pressure or a systolic pressure ≥140 mmHg after repeated measures during one visit. Blood pressure should be repeated at appropriate times within the visit.
- 5. Jugular venous distention- visible bulging of the external jugular veins on either side of the neck
- 6. New onset heart murmur
- 7. Pulmonary rales an abnormal respiratory sound heard during auscultation of the lungs, which is also described as a crackle.
- 8. Tachycardia a persistent HR >30% above the screening value and unrelated to exercise, exertion or anxiety. Heart rate should be repeated at appropriate times within the visit.
- 9. Signs that could indicate right ventricular failure:

Peripheral edema

Ascites

Syncope

Decompensated right ventricular failure – symptoms include shortness of breath, frequent coughing especially when lying flat, abdominal swelling and pain, dizziness, fainting, and fatigue

### 10. Signs on ECHO indicative of potential valvulopathy

Valve regurgitation (aortic or mitral)

Moderate or severe valve regurgitation (tricuspid or pulmonary)

Mean Mitral valve gradient ≥ 4 mmHg

Mean Aortic valve gradient ≥ 15 mmHg

Mean Tricuspid valve gradient ≥ 4 mmHg

Peak Pulmonary valve gradient ≥ 21 mmHg

#### 11. Signs on ECHO indicative of pulmonary hypertension

- a. Tricuspid Regurgitation Jet velocity > 2.8 msec with or without the following findings OR
- b. One of the following findings in the absence of being able to measure Tricuspid Regurgitation Jet velocity:
  - i. Change in right ventricle/left ventricle basal diameter ratio > 1.0
  - ii. Right ventricular acceleration time < 100 msec
  - iii Dilatation of the inferior caval vein (diameter>21 mm and <50% inspiratory decrease) and/or right atrium
  - iv. Change in the geometry of the interventricular septum in systole (flattening) with left ventricular eccentricity index >1.1 in systole and/or in diastole
  - v. Early diastolic pulmonary regurgitation velocity > 2.2 m/sec
  - vi. Tricuspid Anular Plane Systolic Excursion below 18 mm or below Z-score –2

Confidential Page 73 of 175

### Table 10: Adverse Events of Special Interest (continued)

			
Metabolic/Endocrine			
1.	Elevated prolactin level ≥2x above the upper limit of normal (ULN)		
2.	Galactorrhea		
3.	Gynecomastia		
4.	Increase in fasting serum blood glucose ≥2x ULN		
5.	Hypoglycemia – serum blood glucose more than 20% below the glucose level on Study Day -1 value or more than 10% below LLN (reference range $60-140\mathrm{mg/dL}$ )		
Neuropsychiatric			
1.	Serotonin syndrome (At least 3 of following symptoms must be present: Agitation, restlessness,		
	confusion, both increased HR and blood pressure, dilated pupils, muscle twitching, muscle rigidity,		
	hyperhidrosis, diarrhea, headache, shivering, tremors, both nausea and vomiting)		
2.	Hallucinations		
3.	Psychosis		
4.	Euphoria		
5.	Mood disorders: depression and anxiety if they rise to a level of a disorder		
6.	Suicidal thoughts, ideation or gestures		
Genitourinary			
1.	Priapism		

# 8.1.4 Adverse Events Requiring Hospitalization

If a subject is treated in a medical facility (hospital, emergency room, free-standing clinic) related to the occurrence of any AE, the following data will be collected to model health care utilization in patients with Dravet syndrome: AE/reason for hospitalization/clinic visit; duration of the visit in hours/days; admission to intensive care unit; and name/number of procedures performed, including but not limited to, electroencephalogram, ECG, ECHO, positive emission tomography (PET) scan, magnetic resonance imaging (MRI), x-ray, computed tomography CT) scan, surgery, and lumbar puncture/spinal tap.

# 8.2 SEVERITY OF ADVERSE EVENTS

The severity of AEs (whether nonserious or serious AEs) is to be assessed by the investigator as follows (Table 11).

Confidential Page 74 of 175

**Table 11:** Severity Definition of Adverse Events

Severity	Definition
Mild:	A type of AE that is usually transient and may require only minimal treatment or therapeutic intervention. The event does not generally interfere with usual activities of daily living.
Moderate:	A type of AE that is usually alleviated with additional specific therapeutic intervention. The event interferes with usual activities of daily living, causing discomfort but poses no significant or permanent risk of harm to the research participant.
Severe:	A type of AE that interrupts usual activities of daily living, or significantly affects clinical status, or may require intensive therapeutic intervention.
CDISC SDTM S	everity Intensity Scale for Adverse Event Terminology

# 8.3 CAUSALITY OF ADVERSE EVENTS

The causal relationship of an AE to IMP must always be assessed by the investigator. All AEs will be classified as either **related** or **not related** to IMP. If a causality assessment is not provided for an AE (including an SAE), that AE will be considered as related to IMP.

The degree of certainty with which an AE is attributed to IMP or an alternative cause (eg, natural history of the underlying disease, concomitant medication) will be determined by how well the event can be understood in terms of:

- Known pharmacology of ZX008
- Clinically and/or pathophysiologically plausible context
- Reaction of a similar nature previously observed with similar products, or reported in the literature for similar products as being product related (eg, headache, facial flushing, pallor)
- Plausibility supported by the temporal relationship (eg, the event being related by time to administration or termination of treatment with IMP drug withdrawal or reproduced on rechallenge)

The following classifications should be used in categorization of relatedness:

1. Not Related: Concomitant illness, accident or event with no reasonable association

with study drug.

2. Related: The event follows a reasonable temporal sequence from administration of

study drug and is definitive pharmacologically; cannot to be attributed to concurrent disease or other factors or medications. A clinically reasonable response should be observed if the study drug is withdrawn or dose

reduced.

Confidential Page 75 of 175

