### 5.7 PRIOR AND CONCOMITANT MEDICATION

All medications taken by a subject during the Screening and Baseline Seizure Assessment Periods are regarded as prior therapy and must be documented in the eCRF. Significant medications (eg, antibiotics) taken within 30 days prior to the Screening visit should also be captured. All prior and concomitant AEDs will be collected in the CRF.

All medications taken by a subject after the first administration of IMP are regarded as concomitant medication and must be documented in the eCRF, including over-the-counter medication, herbal and vitamin/supplement preparations. Subjects are required to take at least one concomitant AED during the study. All subjects will continue to receive their existing AED(s) with the same doses throughout the study. Every effort should be made to ensure that the regimen of existing medications remains stable during the study; any changes must be discussed with the sponsor prior to implementation. If a decrease in a concomitant AED is necessary to manage an AE, this must be discussed with the sponsor as soon as possible after implementation if not before implementation. Non-study medications and therapies that are considered necessary for the subject's welfare and will not interfere with the response to the study medication may be given at the discretion of the investigator, informing the Medical Monitor as soon as possible.

It should be noted for any subject receiving hypoglycemic agents, the investigator should consider diabetic medication changes in the setting of weight loss and hypoglycemia.

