# 8.7 REPORTING OF SERIOUS ADVERSE EVENTS BY INVESTIGATOR TO IEC/IRB

The timeframe within an IEC/IRB must be notified of a death or an unexpected SAE considered at least possibly related to the IMP is stipulated by each individual IEC/IRB. The investigator is

Confidential Page 77 of 175

responsible for complying with the requirements for IEC/IRB notification. The investigator will notify the relevant IEC/IRB within the applicable timeframe by forwarding the safety report (eg, MedWatch/CIOMS form) completed by the sponsor for the notifiable event.

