# 10.5.2 Safety Analyses

Summaries of safety data will be presented by treatment – ZX008 0.8 mg/kg/day, ZX008 0.2 mg/kg/day or placebo – separately for the Titration, Maintenance and T+M periods. The number and percentage of subjects in each treatment group with AEs will be displayed by body system and preferred term using the Medical Dictionary for Regulatory Activities (MedDRA). Summaries of AEs by severity and relationship to study drug will also be presented. A separate summary will be provided for all serious AEs (SAEs). Selected summaries will be repeated broken out by age group, ie, for ages <6 years and ≥6 years.

Hematology and chemistry laboratory results will be summarized using shift tables that tabulate the

Confidential Page 85 of 175

proportion of subjects who have lab results that change from baseline. Shift tables will be presented for each time point where lab results are collected. Mean change from baseline will also be calculated for continuous hematology and chemistry results at all time points available.

Laboratory tests, vital signs, physical examinations, neurological examinations, ECG, Doppler echocardiogram, C-SSRS, Tanner Staging results, etc, will be summarized appropriately, by treatment. All safety summaries will be based on the SAF Population.

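### The two causality grades in Section 8.3 leave no place for an adverse event with a reasonable but uncertain link to study drug, and they do not match the reporting thresholds in 8.7, 8.4 and 8.6.

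*Protocol*

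**What the plan says.** Section 8.3 sets a two-grade scale: "All AEs will be classified as either related or not related to IMP".

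- **Not Related** is defined as "Concomitant illness, accident or event with no reasonable association" with study drug.
- **Related** needs a reasonable temporal sequence from administration of "study drug and is definitive pharmacologically; cannot to be attributed to concurrent disease or other factors or medications". The definition adds that a clinically reasonable response should be seen on withdrawal or dose reduction.
- **Missing assessments** have a default: "If a causality assessment is not provided for an AE (including an SAE), that AE will be considered as related to IMP".

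Before the definitions, 8.3 says that attribution is a matter of degree of certainty and lists four considerations: known pharmacology, plausible clinical context, reactions to similar products, and timing.

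The grade is used in Section 10.5.2: "Summaries of AEs by severity and relationship to study drug will also be presented". The synopsis plans the same summaries. Section 8.7 describes IEC/IRB notification of a death or an "unexpected SAE considered at least possibly related to the IMP". On background treatment, Section 5.7 states: "Subjects are required to take at least one concomitant AED during the study".

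**The concern.** A two-grade scale works only if the second grade is the complement of the first. Here *Related* sits at the level of a definite relationship with no rival explanation, and *Not Related* at no reasonable association. The ground between them is where many events in this trial could fall. Every subject has Dravet syndrome and takes at least one other antiepileptic drug, so a rival explanation by disease or medication is always available to be considered.

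At stake is the meaning of the related-event tables. The grade is fixed when the investigator records it, so no analysis plan can later recover how an uncertain event would have been graded under a clear rule.

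**Working it through.** No arithmetic applies. The check is whether the two definitions cover every event, and whether other sections use the same threshold.

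**1. Coverage of the 8.3 scale.** Sort events by whether a reasonable association exists and, if so, whether it is definitive with no alternative attribution.

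| Event | Meets *Not Related*? | Meets *Related*? |
|---|---|---|
| No reasonable association | Yes | No |
| Reasonable association, definitive, no alternative cause | No | Yes |
| Reasonable association, but uncertain or with an alternative cause | No | No |

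The third row has no grade, yet 8.3 requires one. The definitions do not carry through the gradation implied by the four considerations that precede them.

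**2. Whether the third row is populated.** Section 5.7 guarantees a concomitant antiepileptic drug in every subject. It also foresees lowering such a drug to manage an adverse event, so the protocol itself treats these drugs as candidate causes. Section 8.1.1 counts a worsening of seizures beyond the subject's usual fluctuation as an adverse event, and the underlying disease is an obvious alternative cause for that.

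**3. Whether the missing-assessment default closes the gap.** It applies when no grade is given. An uncertain event that has been given a grade is not missing.

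**4. Agreement with other thresholds.**

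- **8.7** refers to a possible relationship. The 8.3 scale has no such grade, and its *Related* definition excludes it.
- **8.4** requires a late SAE to be reported to the sponsor if some association with study drug is conceivable, whatever the investigator's view of causality, and points to 8.6.
- **8.6** ties immediate reporting of late SAEs to a judgement that the event is causally related.

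An SAE can therefore meet the 8.4 trigger and not the 8.6 trigger.

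**5. What depends on the grade.**

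| Output or process | Depends on the 8.3 grade? |
|---|---|
| Summaries by relationship (synopsis, 10.5.2) | Yes |
| Adverse event counts by arm; summary of all SAEs (10.5.2) | No |
| On-study SAE reporting to the sponsor or Medical Monitor (8.6) | No, all SAEs |
| Investigator reporting of SAEs to the IRB/IEC (8.6.1) | No, all SAEs |
| Late SAEs under 8.4 | No |
| Late SAEs under 8.6 | Yes |
| Central ECHO reading and follow-up (3.7.2, 8.9.1); 72-hour reports (8.8) | No |

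**The case against.** The strongest reply is that the wording is loose but little follows from it, and much of that stands.

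- **Direction.** A reader might infer that the scale demonstrably under-counts related events. The documents do not support that. An uncertain event fails *Not Related* too, so an investigator could resolve the gap either way. The text shows ambiguity, with under-counting as one possible result.
- **Lost SAEs.** A reader might infer that SAEs go unreported. They do not: on-study SAEs go to the sponsor regardless of causality, 8.6.1 sends all SAEs to the IRB/IEC, and 8.4 catches late SAEs whatever the causality judgement. The mismatch with 8.7 is one of terms.
- **Cardiac harm.** Given the drug's market history (Section 1.2), a reader might infer that a valve signal could be hidden. ECHOs are read centrally with expert adjudication, the ECHO events of special interest in Table 10 are defined by findings and thresholds, and the 72-hour rule in 8.8 carries no causality test.
- **Rival causes.** Background antiepileptic drugs must be stable for at least 4 weeks before screening and continue unchanged, which weakens them as an explanation for an event first seen on study drug. Some events also fit the drug's known pharmacology: Section 1.2 records its use as an appetite suppressant. It would be too strong to say that nearly every event has a convincing alternative cause.
- **Sites.** Differing habits across about 30 sites do not by themselves bias a blinded, randomised comparison of arms.

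What remains is that 8.3 demands a grade its definitions cannot supply, and the protocol plans to tabulate that grade.

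**Conclusion.** The point holds in limited form. The 8.3 definitions are not exhaustive. Events with a reasonable but uncertain link to study drug can be under-counted as related, and nothing in the text makes different investigators grade them alike. The damage is to the interpretation of the summaries by relationship to study drug. Total adverse event and SAE counts by arm, and the randomised comparison of them, are intact.

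The size cannot be stated, because the protocol gives neither adverse event rates nor the share of uncertain attributions. The conclusion assumes that investigators apply the definitions as written and that at least some events have a plausible rival cause, which Sections 5.7 and 8.1.1 themselves anticipate.

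Separately, 8.3 conflicts with 8.7 on the causality threshold, and 8.4 conflicts with 8.6 on which late SAEs are reportable. These sections need to be reconciled. The whole is worth correcting, but it does not threaten the trial's safety oversight.

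**What to change.** 1. In 8.3, define *Related* as a reasonable possibility that study drug caused or contributed to the event, including when disease or another medication is an alternative explanation. Define *Not Related* as its complement, so that every event has exactly one grade.
2. Treat the response to withdrawal or dose reduction as supporting evidence, not as a condition.
3. Use the same term in 8.7.
4. Reconcile the late-SAE rules in 8.4 and 8.6 so that they state one trigger.
5. Put the definition in the eCRF completion guidance.

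The cost is a wording amendment and site guidance, with no new data or visits. The downside is that more adverse events will be graded related, so the tabulated related-event rates will look less favourable.

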# 8.4 OBSERVATION PERIOD FOR ADVERSE EVENT REPORTING

The observation period for AE and SAE reporting in an individual subject will start at the time of giving written informed consent for participation in the current study and finish 15 days after the last dose of study drug or the last visit, whichever is later. For subjects who enroll in the open-label extension study, ongoing AEs will be followed in that study.

If the investigator becomes aware of an SAE that has started after the observation period has finished, and the event could in some way be associated with IMP (irrespective of whether or not it is considered by the investigator to be causally related to IMP), then this must also be reported to the sponsor (see Section 8.6).

### 8.5 ADVERSE EVENT REPORTING

#### **8.5.1** Adverse Events

At each clinical evaluation, the investigator (or delegate) will determine whether any AEs have occurred. Adverse events will be recorded in the AE page of the eCRF. If known, the medical diagnosis of an AE should be recorded in preference to the listing of individual signs and symptoms. The investigator must follow up on the course of an AE until resolution or stabilization. If an AE is ongoing after the end of study visit, the AE will continue to be followed up until resolution or stabilization.

If, during the study period, a subject presents with a pre-existing condition that was not noted at the time of study entry, the condition should be retrospectively recorded in the Medical History section of the eCRF.

#### 8.6 SERIOUS ADVERSE EVENTS REPORTING

This study will comply with all applicable regulatory requirements and adhere to the full requirements of ICH Topic E2A (Clinical Safety Data Management: Definitions and Standards for Expedited Reporting [1994]).

In the event of a SAE the investigator or delegate must:

- Enter all relevant information in the AE page of the eCRF
- 2. Inform the Medical Monitor or the Sponsor of the SAE via email or telephone within 24 hours of becoming aware of the SAE.
- 3. Follow the initial notification with a completed SAE report form. The SAE form must be emailed or faxed to iHC within 24 hours of becoming aware of the SAE.

All SAEs that occur during the course of the study, beginning the day Informed Consent is signed, whether or not causally related to IMP must be reported immediately via telephone or email (within 24 hours of the investigator becoming aware of the event) to the sponsor or the Medical Monitor.

Adverse events occurring in the period between the time the subject gave written informed consent and the first exposure to IMP that meet one or more of the seriousness criteria for AEs must be

Confidential Page 76 of 175

reported to the sponsor and the Medical Monitor in the same manner as other SAEs and will be included in the clinical study database.

Any SAE that occurs 15 days after the last dose of study drug or the last visit, whichever is later that is considered to be causally related to IMP must be **reported immediately (i.e., within 24 hours of the investigator becoming aware of the event) to the sponsor and the Medical Monitor.** 

Contact details and guidance for reporting SAEs will be provided to study site before the study starts.

#### 8.6.1 Requirements for Immediate Reporting of Serious Adverse Events

The minimum reporting requirements for immediate reporting of SAEs include:

- 1. Identifiable subject
- 2. Suspected drug product
- 3. Event description
- 4. Identifiable reporting source In

addition, the investigator must:

- 1. Report all SAEs to the relevant IRB/IEC within the timeframe specified by the IRB/IEC.
- 2. Submit follow-up reports to the sponsor Global Clinical Safety and Pharmacovigilance and the Medical Monitor until the SAE has resolved, or, in the case of permanent impairment, until stabilized.
- 3. Ensure that the AE term(s) and causality assessment for all SAEs is entered in the eCRF.

If the minimum requirements for reporting are fulfilled, the investigator should not wait to receive additional information to fully document the event before notifying the sponsor.

When submitting SAE reports to the sponsor, subjects should be identified only by their subject number and study number. The investigator should not include the subject's name and address.

SAE Update reports can be submitted to the sponsor any time that additional relevant information becomes available. In cases of death, the investigator should supply the sponsor and the IEC/IRB (as applicable, see Section 8.7) with any additional requested information as it becomes available (eg, autopsy reports and detailed medical reports). Once an SAE is reported to the sponsor's Safety Group, a Safety Specialist may contact the investigator with follow-up questions.

The procedure to be followed if an ongoing AE becomes an SAE after the end of the observation period for AEs is described in Section 8.9.

